### 1.2.7 Pharmacodynamics/Biomarkers

Predictive biomarkers within baseline tumor tissue or in the peripheral blood are a research priority shared across all immuno-oncology studies. The identification of reliable biomarkers that can predict either response or toxicity may enhance individualized treatment decisions. The expression of PD-L1 by immunohistochemistry in malignant and surrounding inflammatory cells has been demonstrated as a predictor of response to PD-1 inhibitors in various studies. In lymphoma, however, the expression of PD-1 is present on both malignant cells as well as non-malignant cells in the tumor microenvironment. Further, expression of PD-1 is expected in the majority of cases, so simply the presence or absence may not predict for response. Therefore, localization of PD-1 staining will be assessed on this study as well as longitudinal sampling on optional biopsies taken during therapy and at the time of progression.

Currently, there is an incomplete understanding of the molecular pathways that are susceptible to inhibition of PD-1. A molecular profile may exist that identify patients likely (or unlikely) to respond to PD-1 inhibition. In a study of patients with relapsed Hodgkin lymphoma, pre-treatment tumor specimens from multiple patients revealed copy-number gains in PD-L1 and PD-L2 and increased expression of these ligands. In patients with lung cancer, the number of non-synonymous mutations in the pre-treatment biopsy specimen predicted likelihood of response to PD-1 inhibitor. In melanoma, the absence of PTEN expression has been associated with a lack of clinical response to PD-1 inhibitors. A comprehensive molecular profile will be used on baseline and sequential tumor samples and utilize DNA/RNA sequencing as well as copy number alterations as part of the exploratory analysis to identify genetic profiles of tumors that are likeliest to respond to pembrolizumab.

Another research priority is to identify potential biomarkers in the peripheral blood and CSF that correlate with response or toxicity. A recent study demonstrated that PD-1 inhibitors result in an increase in the number of CD8+Ki-67+PD-1+ effector T-cells in the peripheral blood shortly after initiation of therapy in patients with lung cancer. We will use multi-parameter flow cytometry for T-cell and NK-cell subsets and monitor the peripheral blood for an early host adaptive immune response (6 weeks), a “rebound effect” (18 weeks), at 1 years, and 2 years. In addition, we will assess the host immune response at the time of disease progression. In the case of patients with PCNSL, these tests will also be performed longitudinally in the CSF and correlated with response. Tissue biopsy specimens and peripheral blood samples obtained while on pembrolizumab therapy may identify other potential biomarkers that predict response and/or help elucidate the mechanisms of treatment resistance at the cellular level.

## **2 ELIGIBILITY ASSESSMENT AND ENROLLMENT**

### **2.1 ELIGIBILITY CRITERIA**

#### **2.1.1 Inclusion Criteria**

2.1.1.1 Patients must have a diagnosis of B-cell lymphoma confirmed by Laboratory of Pathology, NCI, that is relapsed from or refractory to prior therapy as follows:

- **Cohort 1:** B-cell lymphoma, unclassifiable, with features intermediate between diffuse large B-cell lymphoma and classical Hodgkin lymphoma (i.e., Gray-zone lymphoma or GZL)
- **Cohort 2:** Extranodal diffuse large B-cell lymphoma involving one or more of the specified extranodal sites (i.e., extranodal DLBCL). The following subtypes are included (they do not have to be confirmed as non-GCB subtype for study entry):
  - Primary CNS lymphoma (PCNSL)
  - Primary testicular lymphoma (PTL)
  - Primary breast lymphoma (PBL)
  - Primary cutaneous DLBCL, leg-type
  - Intravascular large B-cell lymphoma (IVBCL)
  - Diffuse large B-cell, NOS, activated B-cell type, involving 1 or more extranodal site

**NOTE:** For GZL, diagnosis will be in accordance with the 2016 World Health Organization classification of lymphoid malignancies. Patients diagnosed with other extranodal DLBCL subtypes or that are not otherwise specified (NOS) must be involved at least 1 extranodal site and must be considered non-GCB by local immunohistochemistry algorithms. Cases that are non-GCB by the Hans criteria are considered eligible as well as cases of DLBCL that are both CD10+ and MUM1+.

2.1.1.2 Evaluable disease by clinical exam (i.e., palpable lymphadenopathy, measurable skin lesions, etc.), laboratory assessment (i.e., lymphoma involvement of bone marrow or peripheral blood by morphology, cytology or flow cytometry), and/or imaging (measurable lymph nodes or masses on CT or MRI and/or evaluable FDG-avid lesions on PET)

2.1.1.3 Adequate tumor tissue (archival or fresh) must be available for correlative studies.  
**NOTE:** Tumor tissue may be from any previously collected tissue and adequacy is at the discretion of the Principal Investigator. If prior tissue is not available, patient must be willing to undergo baseline tumor biopsy.

2.1.1.4 Be  $\geq$ 18 years of age on day of signing informed consent

2.1.1.5 Adequate performance status (PS) as follows (see APPENDIX A):

- Patients  $\geq$  18 years must have ECOG PS 0-1 and Karnofsky  $\geq$  60%.

**NOTE:** Patients  $\geq$  18 years with an ECOG PS of 2 and Karnofsky  $\geq$  60 will be considered eligible at the discretion of the Principal Investigator if decreased ECOG performance status is felt to be related to residual neurologic deficits caused by CNS disease involvement that are not progressive or anticipated to cause clinical management problems during study participation.

2.1.1.6 Adequate organ function as evidenced by the following laboratory parameters (unless related to lymphoma infiltration at the discretion of the investigator):

• Absolute neutrophil count (ANC)	≥ 750 /mcL
• Platelets	≥ 50,000 / mcL (transfusions not permitted)
• Hemoglobin	≥ 9 g/dL (transfusions permitted)
• Serum creatinine	Adults: ≤ 1.5 X upper limit of normal (ULN) Children age ≥14: ≤ 1.5 mg/dL
OR Measured or calculated creatinine clearance (GFR can also be used in place of creatinine or CrCl) ≥ 30 mL for subject with creatinine levels > 1.5 X institutional ULN (CrCl should be calculated per institutional standard)	
• Serum total bilirubin	≤ 1.5 X ULN OR Direct bilirubin ≤ ULN for patients with total bilirubin levels > 1.5 ULN
• AST (SGOT) and ALT (SGPT)	≤ 3 X ULN (≤ 5 X ULN if liver involvement)

2.1.1.7 The effects of pembrolizumab on the developing human fetus are unknown. For this reason, the following measures apply:

- Women of childbearing potential must have a negative serum or urine pregnancy test within 72 hours prior to the first dose of pembrolizumab.
- Men and women of childbearing potential (WOCBP) who are sexually active must agree to adequate contraception (hormonal or barrier method of birth control; abstinence) prior to study entry, for the duration of study participation, and for at least 120 days after the last dose of pembrolizumab as outlined in Section 4.3.2 and 4.3.3. Should a woman become pregnant or suspect she is pregnant while she or her partner is participating in this study, she should inform her treating physician immediately.
- Participants must not be planning to conceive or father children within the projected duration of the trial, starting with the pre-screening/screening visit through 120 days after the last dose of pembrolizumab.
- WOCBP is defined as any female who has experienced menarche and who has not undergone successful surgical sterilization or who is not postmenopausal. **NOTE:** See Section 4.3.2 for definitions.

2.1.1.8 Ability of patient or Legally Authorized Representative (LAR) to understand and the willingness to sign a written informed consent document

## 2.1.2 Exclusion Criteria

2.1.2.1 Patients with DLBCL who best fit the criteria of EBV+ DLBCL, NOS are not eligible

2.1.2.2 Current or prior anti-cancer treatment prior to the first dose of pembrolizumab as defined below:

- Chemotherapy, targeted small molecule therapy, or other anti-cancer treatment not otherwise specified below within 2 weeks
- Radiation therapy within 2 weeks
- Anti-cancer monoclonal antibody (mAb) treatment within 4 weeks

- Use of an investigational agent (e.g., biologic, drug, or other) within 4 weeks
- Allogeneic stem cell transplant within 100 days
- Prior therapy with an anti-PD-1, anti-PD-L1, or anti-PD-L2 agent at any time

2.1.2.3 No current use of systemic corticosteroids at physiologic doses  $> 10$  mg/day of dexamethasone or equivalent are permitted. Patients receiving current systemic steroids must be on a stable steroid dose (i.e.,  $\le 10$  mg/day of dexamethasone or equivalent at the same dose for at least 7 days). Patients who recently discontinued systemic steroids must have completed them at least 7 days prior to entry.

2.1.2.4 Uncontrolled intercurrent illness including, but not limited to the following that may limit interpretation of results or that could increase risk to the patient at the discretion of the investigator:

- Active autoimmune disease that has required systemic treatment in the past 2 years (i.e., with use of disease modifying agents, corticosteroids or immunosuppressive drugs). **NOTE:** Replacement therapy (e.g., thyroxine, insulin, or physiologic corticosteroid replacement therapy for adrenal or pituitary insufficiency, etc.) is not considered a form of systemic treatment.
- History of (non-infectious) pneumonitis that required steroids, evidence of interstitial lung disease or active, non-infectious pneumonitis.
- Clinically significant history of liver disease, including viral or other hepatitis, current alcohol abuse, or cirrhosis; as well as active infection with HBV or HCV:
  - Patients with occult or prior HBV infection (defined as positive total hepatitis B core antibody [HBcAb] and negative HBsAg) may be included if HBV DNA is undetectable.
  - Subjects who are positive for HCV antibody must be negative for HCV by polymerase chain reaction (PCR) to be eligible for study participation.
- Uncontrolled and/or symptomatic thyroid disease
- Active graft-vs-host disease (GVHD) requiring treatment or any history of  $\ge$  grade II acute GVHD
- Seizure activity within the past 4 weeks
- Known mental or physical illness that would interfere with cooperation with the requirements of the trial or confound the results or interpretation of the results of the trial and, in the opinion of the treating investigator, would make the patient inappropriate for entry into the study.

2.1.2.5 Because there is an unknown but potential risk for adverse events in nursing infants secondary to treatment of the mother with pembrolizumab, breastfeeding must be discontinued if the mother is treated with pembrolizumab

2.1.2.6 Received a live vaccine within 30 days of planned start of study therapy. **NOTE:** Seasonal influenza vaccines for injection are generally inactivated flu vaccines and are

allowed; however intranasal influenza vaccines (e.g., Flu-Mist®) are live attenuated vaccines, and are not allowed.

2.1.2.7 History of allergic reactions attributed to compounds of similar chemical or biologic composition to pembrolizumab unless felt to be in the best interests of the patient in the opinion of the investigator

2.1.2.8 Known additional malignancy that requires active systemic treatment

#### 2.1.3 Recruitment Strategies

This protocol may be abstracted into a plain language announcement posted on NIH websites and NIH Social Media platforms. Study participants will be recruited from the population of patients screened in the lymphoid malignancies clinic of the National Institutes of Health. These will include both referrals from outside physicians as well as patient self-referrals.

### 2.2 SCREENING EVALUATION

**Note:** Screening evaluation testing/procedures are conducted under the separate screening protocol, 01-C-0129 (Eligibility Screening and Tissue Procurement for the NIH Intramural Research Program Clinical Protocols).

**NOTE:** Assessments and procedures to confirm study eligibility should be completed within 28 days prior to registration confirmation/verification (unless otherwise noted).

#### 2.2.1 Clinical Evaluations

- Disease history, including: diagnosis, treatment (e.g., systemic treatments, radiation and surgeries), status, and significant prior/ongoing side effects and symptoms
- Complete medical history, including: all active conditions considered to be clinically significant by the treating investigator
- Physical examination, including: height (screening only), weight, vital signs (i.e., temperature, pulse, respiratory rate, and blood pressure); review of concomitant medications and symptoms/side effects; and, assessment of performance status

#### 2.2.2 Laboratory Evaluations

**NOTE:** Results from outside NIH are accepted.

- CBC with differential
- Chemistry panels (as noted) or specific analyte required for eligibility, including: Creatinine (i.e., or Acute Care Panel); ALT, AST, total and direct (if required) bilirubin (i.e., or Hepatic Panel); and, 24-hour urine creatinine clearance (if needed to measure CrCl in cases where serum creatinine >1.5mg/dl)
- Thyroid function tests, including: thyroid stimulating hormone (TSH), total triiodothyronine (T3), free thyroxine (T4)
- Hepatitis B surface antigen (HBsAg), Hepatitis B core antibody, Hepatitis C antibody (HCV) [qualitative]] (3 months)
- Urine and/or serum HCG in women of childbearing potential (within 3 days prior to initiation of study therapy)

#### 2.2.3 Imaging Studies

**NOTE:** Results from NIH only.

- CT chest, abdomen and pelvis
- MRI of brain (required in patients with PCNSL; as clinically indicated in other patients – i.e., known or suspected involvement of CNS)

#### 2.2.4 Other Procedures

- Pathologic review/confirmation of diagnosis by Laboratory of Pathology, NCI (no time limit). A tissue sample is required for this evaluation; if archival sample is not available, a fresh tumor biopsy will be obtained. If a biopsy procedure is attempted, but tissue is not able to be obtained for any reason (e.g., safety reasons), patient may still be eligible for enrollment at the discretion of the Principal Investigator.

### 2.3 PARTICIPANT REGISTRATION AND STATUS UPDATE PROCEDURES

Registration and status updates (e.g., when a participant is taken off protocol therapy and when a participant is taken off-study) will take place per CCR SOP ADCR-2, CCR Participant Registration & Status Updates found [here](#).

### 2.4 TREATMENT ASSIGNMENT PROCEDURES

#### 2.4.1 Cohorts

Number	Name	Description
1	Gray-zone lymphoma	B-cell lymphoma, unclassifiable, with features intermediate between diffuse large B-cell lymphoma and classical Hodgkin lymphoma (so-called GZL)
2	Extranodal diffuse large B-cell lymphoma	Extranodal DLBCL that involves one or more extranodal sites

#### 2.4.2 Arms

Number	Name	Description
1	Experimental: Pembrolizumab	Administered intravenously (IV) at a fixed dose of 200 mg every 3 weeks until disease progression or unacceptable toxicity; if ongoing clinical benefit after 24 months, option for treatment interruption and retreatment upon relapse

#### 2.4.3 Treatment Assignment and Randomization/Blinding

Patients are assigned to a group/cohort based upon diagnosis; treatment assignment is single arm, open-label and non-randomized (i.e., subjects in Cohorts 1 and 2 directly assigned to Arm 1).

### 2.5 BASELINE EVALUATION

The following should be performed within 28 days prior to the first dose of pembrolizumab unless other noted; tests performed as part of screening do not need to be repeated if they were performed within the specified window prior to the first dose of pembrolizumab.

#### 2.5.1 Clinical Evaluations

- Medical history (interim)
- Physical examination, including weight, and vital signs (i.e., temperature, pulse, respiratory rate, and blood pressure); review of concomitant medications and symptoms/side effects; and, assessment of performance status (within 14 days)

## 2.5.2 Laboratory Evaluations

**NOTE:** Results from outside NIH are accepted.

- Required within 3 days:
  - Urine and/or serum HCG in WOCBP
- Required within 14 days:
  - CBC with differential
  - Chemistry panels, including: Acute Care Panel (sodium, potassium, chloride, CO2, glucose, BUN, creatinine), Mineral Panel (serum calcium, phosphate, magnesium and albumin), Hepatic Panel (alkaline phosphatase, ALT, AST, total and direct bilirubin), and 24-hour urine creatinine clearance (if needed measure CrCl if serum creatinine >1.5mg/dl)
  - Others: LDH, Uric acid, Total protein
  - Coagulation panel, including: PT/INR and aPTT
  - Thyroid function tests, including: thyroid stimulating hormone (TSH), total triiodothyronine (T3), free thyroxine (T4)
  - Urinalysis (with microscopic examination if abnormal)
- Required within 28 days:
  - HIV antibody (within 3 months allowed)
  - Lymphocyte Phenotype: T, B and NK cell subsets
  - Quantitative serum immunoglobulin (IG) levels
  - Anti-Nuclear Antibody (ANA)

## 2.5.3 Imaging Studies

- CT chest, abdomen and pelvis
- MRI of brain (required in patients with PCNSL; as clinically indicated in other patients)
- 18F-FDG PET/CT

**NOTE:** Results from NIH only. Other body areas may be imaged if clinically indicated.

## 2.5.4 Other Procedures

- Flow cytometry will be performed on peripheral blood for both diagnostic and staging purposes (only NIH results accepted; NCI Laboratory of Pathology)
- Bone marrow aspiration and biopsy, if clinically indicated (within 3 months)
- Lumbar puncture (LP) for cytology and flow cytometry; required in patients with PCNSL and if clinically indicated in other patients (within 3 months)
- Ophthalmologic evaluation (in patients with PCNSL)

## 2.5.5 Research Correlates

**NOTE:** See Section 5 for additional information. The following sample types will be collected for correlative research studies:

- Required: Blood samples and tumor tissue (archival or fresh). Cheek swabs or saliva samples (preferred) may be obtained as a source of germline DNA instead of blood.

**Abbreviated Title:** Pembro in R/R GZL and DLBCL

[figure not shown]
**Version Date:** 03/05/2021

- Optional: Tumor biopsy is required for study entry if archival tissue is not available or adequate; otherwise, this is optional.
- Select patients: CSF samples (i.e., patients with Ommaya or planned procedure)

### 3 STUDY IMPLEMENTATION

#### 3.1 STUDY DESIGN

This is a non-randomized, open-label, single arm, single institution phase 2 study of pembrolizumab in patients with relapsed or refractory GZL or extranodal DLBCL (including PCNSL). The patients with GZL and extranodal DLBCL will be enrolled into two (2) separate, disease-specific cohorts.

↑ Bloods for correlates collected prior to treatment, after cycles 2 and 6, and at approximately months 9, 12, 18, and every 6 months thereafter.

↑ Tissue for correlates collected prior to treatment (archival or fresh); with optional fresh tumor biopsy at baseline, after 2 cycles, and at disease progression.

↑ Disease evaluations will be performed prior to treatment and after initiation of treatment at the same time points as correlate blood sample collection.

#### 3.2 DRUG ADMINISTRATION

Each cycle of treatment is 21 days or 3 weeks. The minimum window between cycles due to scheduling or other administrative reasons is 18 days (i.e., 21 days -3 days).

All patients will receive single-agent pembrolizumab at a fixed dose of 200 milligrams (mg) administered via intravenous (IV) infusion every 21 days (3 weeks). Dosing of pembrolizumab is fixed; not based upon subject weight. Infusions may be done peripherally or via central venous access device, etc.

Pembrolizumab will be administered as a 30-minute infusion. Every effort should be made to target the infusion timing as close to 30 minutes as possible; however, a preferred window of -5/+10 minutes to account for variability of infusion pumps is permitted (i.e., anticipated infusion window of 25-40 minutes).

Treatment will be on an outpatient basis; however, at the investigator's discretion (e.g., for additional monitoring, patient social reasons, etc.), patients may be treated on an inpatient basis. Any cases of planned hospitalization are not considered reportable serious adverse events per Section 7.

No premedications are required; however, may be used in specific patients at treating investigator discretion or as directed per toxicity management.

**NOTE:** The FDA-approved labeling contains additional specific instructions for the preparation of pembrolizumab infusion fluid and administration of infusion solution.

### **3.3 DOSE MODIFICATIONS**

Adverse events (both non-serious [AEs] and serious [SAEs]) associated with pembrolizumab exposure may represent an immunologic etiology. These adverse events may occur shortly after the first dose or several months after the last dose of treatment.

Pembrolizumab must be withheld for all drug-related toxicities and severe or life-threatening AEs as per below. See Section [3.3.1](#) for immune-related event supportive care guidelines, including use of corticosteroids.

For any other, non-immune related AEs/SAEs, the treating investigator may use discretion with regards to dose holds, modifications, and supportive care. **NOTE:** See Section [3.3.3](#) for guidelines and management specific to infusion reaction/infusion-related toxicity,

Dosing interruptions are permitted in the case of medical and/or surgical events or logistical reasons not related to study therapy (e.g., elective surgery, unrelated medical events, patient vacation, and/or holidays). Patients should be placed back on study therapy within 3 weeks of the scheduled interruption, whenever possible. The reason for interruption should be documented in the medical/research records. These interruptions will not be considered protocol deviations.

#### **3.3.1 Immune-Related Toxicity Management**

Patients should receive appropriate supportive care measures as deemed necessary by the treating investigator. Suggested supportive care measures for the management of adverse events with potential immunologic etiology are outlined below (i.e., immune-related adverse events or irAEs). Where appropriate, these guidelines include the use of oral or intravenous treatment with corticosteroids as well as additional anti-inflammatory agents if symptoms do not improve with administration of corticosteroids. Note that several courses of steroid tapering may be necessary as symptoms may worsen when the steroid dose is decreased. For each disorder, attempts should be made to rule out other causes such as metastatic disease or bacterial or viral infection, which might require additional supportive care. The treatment guidelines are intended to be applied when the investigator determines the events to be related to pembrolizumab.

**NOTE:** If after the evaluation the event is determined not to be related, the investigator does not need to follow the treatment guidance (as outlined below). Refer to Section [3.3](#) for dose modification.

It may be necessary to perform conditional procedures such as bronchoscopy, endoscopy, or skin photography as part of evaluation of the event.

### 3.3.2 Immune-Related Adverse Events

#### General Instructions:

1. Corticosteroid taper should be initiated upon AE improving to Grade 1 or less and continue to taper over at least 4 weeks.
2. For situations where pembrolizumab has been withheld, pembrolizumab can be resumed after AE has been reduced to Grade 1 or 0 and corticosteroid has been tapered. Pembrolizumab should be permanently discontinued if AE does not resolve within 12 weeks of last dose or corticosteroids cannot be reduced to  $\leq 10$  mg prednisone or equivalent per day within 12 weeks.
3. For severe and life-threatening irAEs, IV corticosteroid should be initiated first followed by oral steroid. Other immunosuppressive treatment should be initiated if irAEs cannot be controlled by corticosteroids.

Immune-related AEs	Toxicity grade or conditions (CTCAEv4.0)	Action taken to pembrolizumab	irAE management with corticosteroid and/or other therapies	Monitor and follow-up
Pneumonitis	Grade 2	Withhold	

• Administer corticosteroids (initial dose of 1-2 mg/kg prednisone or equivalent) followed by taper

	

• Monitor participants for signs and symptoms of pneumonitis

• Evaluate participants with suspected pneumonitis with radiographic imaging and initiate corticosteroid treatment

• Add prophylactic antibiotics for opportunistic infections

	Grade 3 or 4, or recurrent Grade 2	Permanently discontinue		
Diarrhea/ Colitis	Grade 2 or 3	Withhold	

• Administer corticosteroids (initial dose of 1-2 mg/kg prednisone or equivalent) followed by taper

	

• Monitor participants for signs and symptoms of enterocolitis (ie, diarrhea, abdominal pain, blood or mucus in stool with or without fever) and of bowel perforation (ie, peritoneal signs and ileus).

• Participants with <math>\geq</math> Grade 2 diarrhea suspecting colitis should consider GI consultation and performing endoscopy to rule out colitis.

• Participants with diarrhea/colitis should be advised to drink liberal quantities of clear fluids. If sufficient oral fluid intake is not feasible, fluid and electrolytes should be substituted via IV infusion.

	Grade 4	Permanently discontinue		
AST/ ALT elevation or	Grade 2	Withhold	

• Administer corticosteroids (initial dose of 0.5- 1 mg/kg prednisone or equivalent) followed by taper

	

• Monitor with liver function tests (consider weekly or more frequently until liver

Immune-related AEs	Toxicity grade or conditions (CTCAEv4.0)	Action taken to pembrolizumab	irAE management with corticosteroid and/or other therapies	Monitor and follow-up
Increased bilirubin	Grade 3 or 4	Permanently discontinue	
 
Administer corticosteroids (initial dose of 1-2 mg/kg prednisone or equivalent) followed by taper
 
	enzyme value returned to baseline or is stable
Type 1 diabetes mellitus (T1DM) or Hyperglycemia	Newly onset T1DM or Grade 3 or 4 hyperglycemia associated with evidence of $\beta$ -cell failure	Withhold	
 
Initiate insulin replacement therapy for participants with T1DM
 
Administer anti-hyperglycemic in participants with hyperglycemia
 
	
 
Monitor participants for hyperglycemia or other signs and symptoms of diabetes.
 

Hypophysitis	Grade 2	Withhold	
 
Administer corticosteroids and initiate hormonal replacements as clinically indicated.
 
	
 
Monitor for signs and symptoms of hypophysitis (including hypopituitarism and adrenal insufficiency)
 

	Grade 3 or 4	Withhold or permanently discontinue 		
Hyperthyroidism	Grade 2	Continue	
 
Treat with non-selective beta-blockers (eg, propranolol) or thionamides as appropriate
 
	
 
Monitor for signs and symptoms of thyroid disorders.
 

	Grade 3 or 4	Withhold or permanently discontinue 		
Hypothyroidism	Grade 2-4	Continue	
 
Initiate thyroid replacement hormones (eg, levothyroxine or liothyroinine) per standard of care
 
	
 
Monitor for signs and symptoms of thyroid disorders.
 

Nephritis and Renal dysfunction	Grade 2	Withhold	
 
Administer corticosteroids (prednisone 1-2 mg/kg or equivalent) followed by taper.
 
	
 
Monitor changes of renal function
 

	Grade 3 or 4	Permanently discontinue		
Myocarditis	Grade 1 or 2	Withhold	
 
Based on severity of AE administer corticosteroids
 
	
 
Ensure adequate evaluation to confirm etiology and/or exclude other causes
 

	Grade 3 or 4	Permanently discontinue		

**Abbreviated Title:** Pembro in R/R GZL and DLBCL

**Version Date:** 03/05/2021

Immune-related AEs	Toxicity grade or conditions (CTCAEv4.0)	Action taken to pembrolizumab	irAE management with corticosteroid and/or other therapies	Monitor and follow-up
All other immune-related AEs	Intolerable/persistent Grade 2	Withhold	

Based on type and severity of AE administer corticosteroids

 
NOTE: Events that require discontinuation include and not limited to: Gullain-Barre Syndrome, encephalitis.
	

Ensure adequate evaluation to confirm etiology and/or exclude other causes

	Grade 3	Withhold or discontinue based on the type of event.		
	Grade 4 or recurrent Grade 3	Permanently discontinue		

1. Withhold or permanently discontinue pembrolizumab is at the discretion of the investigator or treating physician.

**NOTE:** For participants with Grade 3 or 4 immune-related endocrinopathy where withhold of pembrolizumab is required, pembrolizumab may be resumed when AE resolves to  $\leq$  Grade 2 and is controlled with hormonal replacement therapy or achieved metabolic control (in case of T1DM).

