### 3.7.1 30-Day Safety Follow-Up Visit

The mandatory Safety Follow-Up Visit should be conducted approximately 30 days after the last dose of trial treatment or before the initiation of a new anti-cancer treatment, whichever comes first. All AEs that occur prior to the Safety Follow-Up Visit should be recorded. Patients with an AE of Grade > 1 will be followed until the resolution of the AE to Grade 0-1 or until the beginning of a new anti-neoplastic therapy, whichever occurs first. SAEs that occur within 90 days of the end of treatment and before initiation of a new anti-cancer treatment should also be followed and recorded. Patients who are eligible for retreatment with pembrolizumab (as described in Section [3.5.3](#)) may have up to two safety follow-up visits, one after the Treatment Period and one after the Second Course Phase.

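### Myocarditis is held from Grade 1, but the general restart rule allows pembrolizumab to resume at Grade 1; a one-line footnote would close the gap

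*Combined protocol and SAP*

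**What the plan says.** Section 3.3 makes the holds in the toxicity table mandatory: "Pembrolizumab must be withheld for all drug-related toxicities and severe or life-threatening AEs as per below". In the table of section 3.3.2, the myocarditis row withholds drug at Grade 1 or 2 and stops it permanently at Grade 3 or 4. On steroids the row says only "Based on severity of AE administer corticosteroids"; it gives no dose, and no grade at which treatment may restart.

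Restart is governed by the general instructions above the table. Instruction 2 applies wherever drug has been withheld: "pembrolizumab can be resumed after AE has been reduced to Grade 1 or 0 and corticosteroid has been tapered". Instruction 1 sets the taper: "Corticosteroid taper should be initiated upon AE improving to Grade 1 or less and continue to taper over at least 4 weeks". Instruction 2 also has a time limit: "Pembrolizumab should be permanently discontinued if AE does not resolve within 12 weeks of last dose". The same limit applies if steroids cannot be brought down to 10 mg of prednisone or equivalent per day.

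The section contains one event-specific restart rule, the NOTE under the table: "For participants with Grade 3 or 4 immune-related endocrinopathy where withhold of pembrolizumab is required, pembrolizumab may be resumed when AE resolves to" Grade 2 or lower with hormonal or metabolic control. It does not cover myocarditis. The table's only footnote attaches to the hypophysitis and hyperthyroidism rows.

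**The concern.** The table treats myocarditis more strictly than other events by holding drug from Grade 1, but the restart rule was not adjusted to match. A patient whose Grade 2 myocarditis falls to Grade 1 meets the general restart condition at a grade that would have required a hold had it been the presenting grade. Two investigators at this single institution could treat such a patient differently and both be following the protocol. What is at stake is re-exposure to the drug while a low-grade immune-related cardiac event persists. No efficacy estimate, sample size or error rate depends on it.

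**Working it through.** There is no stated figure to reproduce. The check compares each row's hold range with the Grade 1 or 0 restart threshold of Instruction 2.

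| Row in section 3.3.2 | Lowest grade held | Does Instruction 2's restart grade fall inside the hold range? |
|---|---|---|
| Pneumonitis | 2 | No |
| Diarrhea/colitis | 2 | No |
| AST/ALT or bilirubin | 2 | No |
| Type 1 diabetes / hyperglycemia | New-onset diabetes: no grade given; hyperglycemia: 3 | Cannot be judged for new-onset diabetes; no for hyperglycemia |
| Hypophysitis | 2 | No |
| Hyperthyroidism | 3 | No |
| Hypothyroidism | Not held | Not applicable |
| Nephritis | 2 | No |
| Myocarditis | 1 | **Yes, at Grade 1** |
| All other immune-related events | 2 (intolerable or persistent) | No |

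Of the 10 rows, 10 − 1 = 9 carry a hold. One of those 9, myocarditis, names Grade 1. Every other hold defined by grade alone starts at Grade 2 or 3, so restarting at Grade 1 or 0 means restarting below the hold range. Applied to myocarditis, the same pattern gives Grade 0.

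**Paths into the gap**

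- *Grade 2 improving to Grade 1.* The grade has been reduced, so Instruction 2 permits restart once any steroid is tapered. This is the clear case.
- *Onset at Grade 1.* Instruction 2 speaks of a grade that has been reduced. That may already require Grade 0, or Grade 1 may count as meeting the threshold. The text does not settle it.
- *Grade 3 or 4.* Drug is stopped permanently, so the gap is not reached.

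**Could other text supply the missing grade?**

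- *The 12-week limit.* It turns on the event resolving, with no grade given. Section 3.7.1 follows adverse events "until the resolution of the AE to Grade 0-1", so the protocol's own usage allows resolution to mean Grade 1. The limit leads only to permanent discontinuation.
- *The endocrinopathy NOTE.* Hypophysitis is held at Grade 2, where the row says "Administer corticosteroids and initiate hormonal replacements as clinically indicated". The NOTE lets Grade 3 or 4 hypophysitis restart at that same grade. There, restarting inside a hold range is written out and tied to control of the event. Myocarditis has no such text.
- *Sections 3.4 and 7.4.1, and Appendix B.* Results are reviewed before each cycle, the principal investigator reviews adverse events on each patient, and a risky rechallenge after a serious event needs the principal investigator's advance approval. None of these sets a grade, and Appendix B refers back to the dose modification guidelines.

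**Timing of a Grade 1 restart.** Let x be the days from Grade 2 to Grade 1, an assumed value because the documents give none. If steroids are given and the taper must be complete, the minimum hold is x + 28 days. For x = 0 to 28 this is 28 to 56 days. With the last dose on day 0, onset on days 1 to 20 and doses due on days 21, 42 and 63, the earliest restart falls between day 1 + 0 + 28 = 29 (one dose missed) and day 20 + 28 + 28 = 76 (three missed). If the steroid condition is instead met at 10 mg of prednisone or less, or if no steroid is given, no minimum hold is stated.

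**The case against.** The strongest reply is that the two rules act in sequence. The row triggers the hold; Instruction 2, which addresses drug already withheld, releases it. The row says nothing about how long the hold lasts, and the mandatory wording in section 3.3 points to everything below it, Instruction 2 included. The NOTE also shows that the authors write out exceptions to Instruction 2, so silence on myocarditis suggests that the general rule applies. This is the natural reading, and it stands. A reader might infer that the protocol contradicts itself, ordering a hold and permitting a dose at the same moment; the documents do not support that. But the sequential reading leaves the point itself in place: the protocol then permits restart at a grade it considers sufficient to stop the drug.

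Three other inferences also go too far:

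- *That no other hold could include Grade 1.* New-onset type 1 diabetes is held without a grade, so the statement is limited to graded rows.
- *That a 28-day gap is guaranteed.* That requires both steroid use and a completed taper, as set out above.
- *That patients are now exposed.* Section 11.2 records early closure to accrual, and the documents do not say whether anyone remains on treatment. Second Course entry under section 3.5.3 also has its own screen for interfering conditions.

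It is also fair to say that no text names Grade 0 for myocarditis, that Appendix B describes Grade 1 as mild or without symptoms, and that restart is a matter of discretion for every held event. Grade 0 is therefore an inference from the table's pattern. If the sponsor wants a Grade 1 restart, it can say so, as it did for endocrinopathies.

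**Conclusion.** The point holds as a cheap improvement in patient safety. Myocarditis is the only graded row where the general restart threshold overlaps the hold range. Under any reading, the protocol allows Grade 2 myocarditis that has improved to Grade 1 to be re-dosed after any steroid taper, and it leaves onset at Grade 1 unclear.

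The size is small. Section 9.2 planned treatment for 48 patients, and with early closure that is an upper bound on those who could ever have been at risk. The documents give no myocarditis incidence, so no frequency is estimated. Few if any patients would be affected. Sample size, power and the primary analysis do not change. The conclusion rests on the wording of section 3.3.2; the assumed hold times bear only on how soon a restart could occur.

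**What to change.** Add one footnote to the myocarditis row in section 3.3.2: *For myocarditis, resume only after resolution to Grade 0 and after any corticosteroid has been tapered; if Grade 0 is not reached within 12 weeks of last dose, permanently discontinue per General Instruction 2.* This uses the existing 12-week limit and, for this event, gives resolution a grade. Events judged unrelated to pembrolizumab are already outside the guidance under section 3.3.1, so no clause for them is needed.

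The cost is one line in an amendment, with no added scheduled visits, tests or patients. The downside is that an occasional patient with persistent Grade 1 myocarditis stays off drug longer or stops.
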